Coaching Caregivers of Children with Spinal Cord Injury

NCT# 03898700

April 2021

Background and Rationale:

Parents of young children serve as caregivers, providing a variety of assistance until youth are able to do tasks and care for themselves on their own. When a child has a chronic health condition, such as a SCI, parents often become lifelong caregivers. A majority of caregivers of youth with SCI are mothers. This caregiving role is associated with poor outcomes in health related quality of life, for example caregivers are at high risk for emotional stress, fatigue, social isolation and frequent episodes of ill health.

Interventions for caregivers of youth with chronic conditions and special needs have been investigated previously, but none for caregivers of youth with SCI.

Occupational Performance Coaching (OPC) is an intervention that provides a framework where professionals specifically coach caregivers to identify and solve issues that are barriers to their performance in their parenting and caregiving roles. Currently there are no studies on OPC in pediatric SCI but it has potential to fill the gap in interventions for caregivers of youth with SCI. OPC may be the intervention to fill this void because it employs problem solving, it focuses on identifying solutions to participation challenges that are associated with the social and physical environments which have been identified as problematic and lastly the evidence on OPC with caregivers of youth with other conditions shows positive outcomes on parent self-efficacy, stress and competency.

Specific Aims:

The specific aim of this study is twofold. First, to establish the feasibility of the OPC for caregivers of youth with SCI, and second to establish standardized methodological procedures for a future multi-center study on the effectiveness of OPC as an intervention for caregivers of youth with SCI.

Within this twofold aim, there are seven study objectives:

1. To determine the degree to which caregivers of youth with SCI believe in their ability to create and achieve meaningful participation goals.
2. To determine the degree to which therapists implement OPC, with fidelity.
3. To determine caregiver and therapist satisfaction and acceptance with OPC.
4. To establish the reliability of the OPC fidelity measure.
5. To determine the degree to which outcome instruments are completed in their entirety, and with accuracy and validity.
6. To establish parameters for a future randomized-controlled trial (RCT) on OPC including dosage and delivery specifications for OPC intervention; sample size estimation; and cost and time requirements for OPC study implementation.
7. To determine the feasibility of randomizing caregivers of youth with SCI into a treatment groups.

Risks and Benefits:

1. The risks involved in this research are minimal. Participants may become bored or tired during the coaching sessions or they may become upset or frustrated. Additionally, there may be a loss of confidentiality. In order to protect against risk, coaches are trained clinicians with experience working with parents of children with SCI. In order to minimize the risk of loss of confidentiality,

an identification number will be assigned to all participants. Identification number and corresponding name will be kept in a secure location separate from any participant data.

2. Potential benefits include an intervention developed specifically to meet the needs of female primary caregivers of children with SCI including but not limited to mothers, grandmothers and aunts surrounding caregiving of a child with a chronic condition. This intervention employs problem solving, which is an approach that has been identified as highly relevant for caregivers with SCI, and one that has shown to be highly effective for caregivers of children with other chronic conditions. Secondly, it explicitly focuses on identifying solutions to participation challenges that are associated with the social and physical environments which are areas identified by children with SCI and their caregivers as being problematic.

Research Strategy

Significance: This study addresses the unmet needs of female primary caregivers of youth with SCI. This is significant in that if these needs are not addressed through interventions that are explicitly designed to empower caregivers in their caregiving and parenting roles, both caregivers of youth with SCI and youth with SCI will remain vulnerable to the well-established adverse implications of information caregiving. This is the first study to establish the feasibility of an intervention explicitly for female primary caregivers of youth with SCI, and it will inform the development of standardized methodological procedures for the use of OPC as an intervention for caregivers of youth with SCI as well as a future RCT that will assess the efficacy of OPC for caregivers of youth with SCI.

Design: A sample of convenience will be used. Following consent and baseline data collection, participants will be assigned to one of two coaching methods, face to face format or phone. Participants who receive coaching over the phone will follow the exact procedures as face to face except coaching will be provided over the phone. The OPC intervention will last up to 10 weeks. Participants will be involved in the study for up to 18 months including baseline data collection, the intervention, and follow up data collection.

Sample: A convenience sample of up to 20 female primary caregivers, including but not limited to mothers, grandmothers and aunts of children with SCI will be recruited from three facilities specializing in pediatric SCI care and rehabilitation using the following inclusion and exclusion criteria:

Inclusion Criteria

1. Female primary caregivers of children with traumatic or acquired, non-progressive SCI between 6 and 13 years of age
2. Female primary caregivers will have legal guardianship of their child with SCI;
3. Speak, read and comprehend English
4. be available for face-to-face visits at a location in close proximity to the coach who will be providing coaching
5. have a cell phone with text messaging capabilities; be willing to utilize cell phone or land line for coaching
6. be able to verbalize challenges in their own participation or their child's participation during initial screening
7. Provide written consent

Exclusion Criteria

1. Severe mental health condition (female primary caregiver) as documented in the child's medical record or reported to research staff by child's treating physician or medical team member
 - a. If potential participants experience emotional distress, a qualified mental health professional will be available to provide appropriate resources or referrals if needed.
 - b. This would be documented in the child's medical record as standard procedure by the qualified mental health professional
2. Abuses or addictions (female primary caregiver) to illicit or prescribed substances or alcohol at the time of screening as documented in the child's medical record or reported to research staff by the child's treating physician or medical team member
3. Have a child with a diagnosis of suspected conversion syndrome at the time of screening as documented in the child's medical record or reported to research staff by the child's treating physician or medical team member
4. Have a child who is suicidal at the time of screening as documented in the child's medical or reported to research staff by the child's treating physician or medical team member
 - a. If suicidal ideation (including intent and/or plan) is communicated at any point research staff will connect the participant with the qualified mental health professional who will conduct a suicide risk assessment and if needed, break confidentiality to call emergency personnel.
 - b. This would be documented in the child's medical record as standard procedure by the qualified mental health professional

Facilities: Three facilities specializing in pediatric SCI care and rehabilitation will recruit for and enroll participants in the study 1) Shriners Hospitals for Children- Chicago 2) Shriners Hospitals for Children – Philadelphia and 3) TIRR Memorial Hermann- Houston. Thomas Jefferson University is the regulatory and lead site, however no participants will be enrolled at this site. Each enrolling site will have 1-2 trained coaches who will each recruit, enroll, and complete the study procedures for data collection with up to 5 participants.

Data Collection and Study Procedures:

1. Following consent, screening, and enrollment, baseline data collection will occur including baseline demographics of caregiver and child characteristics, the Beck Anxiety Inventory, the International Spinal Cord Injury Basic Data Set for Primary Caregivers, and the International Spinal Cord Injury Pediatric Activities and Participation Basic Data Set.
2. Each coach will provide the intervention to up to 5 participants. Participants will be assigned to coaching method based on their order of enrollment. Depending on the coach, the first 1-2 participants enrolled will have face to face coaching. The next 1-3 participants will have phone coaching. Seven female primary caregivers will receive the face to face and 9 will receive the phone coaching, for a total of 16 participants to receive the intervention.
3. In the event that face to face is not feasible, participants will have coaching via phone.
4. Caregivers who are have face to face coaching will receive up to 10 coaching sessions at a location that is mutually convenient for the caregiver and coach.
 - a. The caregiver and coach will decide on how the sessions will be distributed over a 10 week period
 - b. All 10 sessions must be completed within a 10 week period
 - c. Each session will not exceed 90 minutes
 - d. If goals are accomplished before 10 sessions, coaching will cease
 - e. The general content, format and purpose of each coaching session is outlined in Table 1 below.
 - f. All coaching sessions will be audio-recorded for assessment of treatment fidelity
5. Caregivers who are enrolled but who have not started coaching will receive monthly text messages from the project coordinator starting 1 month after enrollment. This is for retaining the participant.
6. The start and stop time of each OPC session will be documented on a study specific CRF that will also include information on caregiver attendance.
7. If coaching sessions are cancelled, rescheduled and/or missed coaches will document the occurrence and the caregivers' reasons for missing the session will be documented.
8. Caregivers who received and finished face to face coaching will be contacted on a monthly basis by the project coordinator via phone and asked about how goal focused problem solving skills have been generalized to other participation challenges and goals. This will be done to keep the caregivers engaged while assessing generalization of skills gained through coaching.
9. Assessments (primary).
 - a. Canadian Occupational Performance Measure: This outcome will evaluate performance of and satisfaction with performance in self-identified goals.

Performance and satisfaction will be rated on a scale between 1-10, where 1 is “cannot perform” “not satisfied” and 10 is “performs without a problem” and “very satisfied”. Goals will be rated by the caregivers before and after coaching.

10. Secondary (exploratory)

- a. Parenting Sense of Competence Scale (PSOC): most widely used measure of parental self-efficacy, it contains 17 items rated on a 6 point scale and evaluates satisfaction with parenting
- b. Parenting Stress Index Short Form-4 (PSI-SF-4): one of the most widely used measures of parental stress, it provides a method to evaluate parent stress with few items. It is comprised of 3 subscales including Parental Distress, Parent-Child Dysfunctional Interaction and Difficult Child as well as a Total Stress Scale.
- c. Pediatric Measure of Participation Short Form (PMoP SF) Parent Report: used to measure a caregiver's perception of their child's participation

11. Satisfaction – following completion of coaching, caregivers will participate in a semi-structured interview to explore satisfaction (Table 2)

Table 1: General Content and Sequence of Coaching Session

Session	General Goals	General Tasks
1	Build rapport, COPM, BIGSS	
 *Identify three participation goals; coach towards caregiver visualizing goals using guided imagery “what would it look like?”, “how do you see it and want it?”
2	Rapport building, goal focused problem solving	
 *Explain goal focused problem solving – review goals, explore options, plan actions, carry out plan, assess outcome *Caregiver selects one goal to apply problem solving, examine strengths, challenges, barriers, requirement of goal. *Define action towards goal *Follow through, agree upon action towards goal
3	Progress toward goal using goal focused problem solving, Begin problem-solving for remaining two goals	
 *Check progress on first goal *Review goals – explore options, plan actions, carry out plan, assess outcome *Identify one, two action step for each goal *Follow through, agree upon action towards goal
4-8	Progress toward goal using goal focused problem solving	
 * Review goals – explore options, plan actions, carry out plan, assess outcome *Check progress, plan action for each goal
9	Progress toward goal using goal focused problem solving	
 Review goals – explore options, plan actions, carry out plan, assess outcome *Check progress, plan action for each goal *Begin to close therapeutic relationship
10	COPM, BIGSS, Identify status of each goal, promote ongoing work, close relationship	
 Review goals – explore options, plan actions, carry out plan, assess outcome *Check progress, plan action for each goal *Close therapeutic relationship, reminder of phone calls

Table 2: Example of Questions for Final Caregiver Satisfaction Interviews

The purpose of the interview is to gather your thoughts and feedback about the Occupational Coaching Intervention that you participated in.	
Questions	Helpful Probes
Can you tell me about the intervention	
 • What did you do during the visits • What did you talk about • What was the coach like • Tell me more about that • Anything else
Tell me about the goals you chose	
 • How did you choose them • Tell me more about that
What did you do to work towards your goals	
 • Did you achieve them • Why do you think you achieved (or did not achieve) them • What helped you move towards your goals • What did not help you move towards your goals • Say more • Anything else
How will you approach future goals	
 • What skills will you take with you • How successful do you think you will be • Tell me more
Was there anything you really liked about the intervention	
 • Tell me about these • What was most helpful • Can you say more about that
Was there anything you disliked about the intervention	
 • Tell me about these • What was most helpful • Can you say more about that • What would you change
Is there anything else you would like to tell me that I may have missed	

Recruitment: Primary female caregivers, including but not limited to mothers, grandmothers and aunts of children with SCI will be identified and recruited from the SCI practices at each facility. A member of the research team at each facility will make personal contact with the potential participant either 1) during their child's scheduled appointment or 2) via phone. Both methods will introduce the study and inquire about interest. If there is interest a contact form will be completed and a future appointment will be scheduled.

Informed Consent Process: Informed consent will be obtained from participants who have the capacity to give informed consent by a member of the research team who is authorized to consent for this study. The process will include a thorough discussion of all the elements outlined in the informed consent document, including but not limited to what is expected to happen during the study, risks and benefits of the planned intervention, and any possible alternatives. Potential participants will be given sufficient time to consider consenting to the study. The participant will be given a copy of the signed consent form. The original consent will be maintained in the participant's study binder/folder and kept in a locked storage cabinet.

Data Storage and Transmission

1. Original Site Data: Data will be recorded on standardized or study-specific case report forms. Participants will be assigned a confidential study identifier. The original data and subject identifiers from each site will be kept in a locked file cabinet, accessible only to the key research staff working on the study.
2. Data Transmission from Participating sites to the Lead Site: All data transmitted from the participating site will be de-identified, and coded with a unique subject identifier. Copies of all de-identified measures, CRFs, and audio recordings will be sent to the lead site via secure upload to a study specific Sharefile Account. The PI and/or project coordinator at the lead site will retrieve all data from the Sharefile account and save it to the designated file on the research drive. Once the data of participating sites are saved, they will be permanently removed from the Sharefile account.

Data Handling and Analysis: All data will be recorded on study specific CRFs and standardized measures and assessments. It will be sent to the lead site following the procedure above and will be entered into a study specific database.

Primary Outcome

1. Canadian Occupational Performance Measure: A 2-point change on the COPM indicates a clinically meaningful change, and 0.9 and 1.9 were found to be optimal cut-off points for performance and satisfaction, respectively. We will examine changes in COPM performance and satisfaction scores using non-parametrics.

Secondary Exploratory

2. BIGSS: We will calculate Spearman rank correlation coefficients (r_s) and create a correlation matrix to examine the relationships among caregivers' confidence in achieving goals, goal attainment (COPM), parent competency, stress, anxiety and participation, parent perceptions of child's participation, and caregiver and child characteristics. We will use these associations to better define inclusion and exclusion criteria for a future RCT on OPC, and to define primary and secondary endpoints for a future RCT.
3. Fidelity: Descriptive and summary statistics will be used to identify the number (mean, mode and range) of coaching sessions conducted for the face-to-face OPC group and the phone OPC group, and the average number and range of sessions required for goal attainment. We will also identify the average time per OPC session for both groups. The number of missed sessions and reasons for missing sessions will be identified. We will examine variability among the four coaches, and will determine if significant differences in these variables exist between OPC face-to-face and phone OPC. These data will be used to define the dosing parameters of OPC for a future RCT.
4. The audio-recordings of each OPC session will be transcribed verbatim. The transcriptions will be read and evaluated on treatment fidelity. Inter-rater reliability on treatment fidelity between the two graduate assistants will be evaluated by calculating intraclass correlation coefficients (ICC, Model 2,1) with 95% confidence intervals (CI). The PI will randomly select 10 transcribed face-to-face OPC sessions and 10 phone OPC sessions, and will also assess

treatment fidelity. Agreement between the assessments of fidelity will serve as an internal quality control, but will also further assess reliability using ICC (2,1) with 95% CI.

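### The plan makes no provision for interviewing caregivers who start coaching and then leave, so the satisfaction findings may rest on completers only

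*Combined protocol and SAP*

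**What the plan says.** Objective 3 under Specific Aims is "To determine caregiver and therapist satisfaction and acceptance with OPC". For caregivers, the instrument is the interview in Data Collection and Study Procedures, item 11: "following completion of coaching, caregivers will participate in a semi-structured interview to explore satisfaction". Table 2 gives example questions for this final interview. It is introduced to the caregiver as a chance to "gather your thoughts and feedback about the Occupational Coaching Intervention that you participated in", and it includes open questions on what she liked, what she disliked and what she would change.

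Completion of coaching is not defined. Sessions run up to 10, and item 4d describes one early end: "If goals are accomplished before 10 sessions, coaching will cease". Item 7 covers cancelled, rescheduled and missed sessions, for which "the caregivers' reasons for missing the session will be documented". The Fidelity paragraph of Data Handling and Analysis adds: "The number of missed sessions and reasons for missing sessions will be identified".

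The documents contain no withdrawal procedure, exit interview or early-termination assessment. They give no analysis method for the interview data.

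**The concern.** This is a feasibility study, and acceptability is one of the things it sets out to learn. A caregiver who tries OPC and drops out has direct evidence on that question. Under item 11 as worded she may never reach the point that triggers the interview, whereas a caregiver who stops early because she met her goals does reach it. If sites follow the literal wording, inclusion in the interview sample depends on having stayed, and staying is plausibly related to finding the coaching acceptable.

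The consequence would be an account of satisfaction that lacks the reasons why OPC did not suit some caregivers. Objective 6 uses this study to set dosage and delivery for a future RCT, so those missing reasons would matter there too. Three sites enrol, and without an instruction each could handle leavers differently.

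**Working it through.** **1. Who reaches the interview.** Set against the ways coaching can end, the plan provides as follows:

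| How coaching ends | Does the plan lead to the interview? |
|---|---|
| All sessions held | Yes (item 11) |
| Goals met early | Yes, on a natural reading of items 4d and 11 |
| Caregiver stops for any other reason | Not stated anywhere |

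**2. Whether anything else fills the gap.**
- The COPM satisfaction score rates performance on self-identified goals, and the PSOC rates satisfaction with parenting (items 9 and 10). Neither rates OPC.
- The monthly calls in item 8 go to caregivers who have finished face-to-face coaching, and they ask about generalising skills.
- Reasons for missed sessions (item 7, Fidelity paragraph) are useful but partial. They are taken session by session and documented by the coach who delivers the intervention. They do not cover the Table 2 questions on dislikes and changes.

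**3. The number treated.** Item 2 states "Seven female primary caregivers will receive the face to face and 9 will receive the phone coaching, for a total of 16 participants". The sum is 7 + 9 = 16, which reproduces the plan's figure. The Sample section allows more recruits: "A convenience sample of up to 20 female primary caregivers".

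**4. Share not heard.** Let w be the number who start and then leave without an interview. The documents give no withdrawal rate, so w is an assumption.

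| w (assumed) | w/16 |
|---|---|
| 0 | 0% |
| 1 | 6.25% |
| 2 | 12.5% |
| 4 | 25% |

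If all 20 were treated, each caregiver would be 1/20 = 5%.

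**5. Direction of any bias.** Suppose, only to see the sign, that satisfaction were a proportion: p_c among completers and p_w among those who left. The difference between what completers show and what holds for all 16 is

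p_c − [(16 − w)·p_c + w·p_w]/16 = (w/16)·(p_c − p_w).

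This is zero if w = 0 or p_w = p_c, positive if leavers are less satisfied, and negative if they are more satisfied. Its size cannot exceed w/16. The plan gives no value for w, p_c or p_w and defines no such proportion, so no figure is put on it here.

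**The case against.** The strongest reply is that item 11 gives a time and does not define a population. It speaks of caregivers without naming a subset, whereas item 8 expressly limits its calls to those who finished. Completion is undefined, the number of sessions is flexible, and the Table 2 introduction fits anyone who attended a session. Nothing tells a site to leave withdrawers out. This stands in part: exclusion is inferred from silence. But a site that reads the wording literally has no instruction to interview a caregiver who leaves, and the timing reading does not say when she would be interviewed.

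A second reply is that disengagement will be visible through attendance records and reasons for missed sessions, and that Table 2 invites criticism. This also stands in part. These features lower the chance that poor acceptance goes unnoticed, but they do not give the views of those who left.

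A reader might go further and infer that acceptance of OPC will be overstated, by so many percentage points. The documents do not support that. Overstatement needs both withdrawals and lower satisfaction among those who withdraw, and neither is given; some may leave for reasons unrelated to OPC. The interview is also qualitative, with no planned acceptance rate or threshold, so percentages and confidence intervals would describe an estimate the study does not intend to report.

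Finally, the study is small and exploratory, and the primary COPM outcome does not depend on this interview. That keeps the point modest. It does not remove it, because objective 3 is one of the seven stated objectives.

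**Conclusion.** The gap is real but limited. The plan provides no interview for caregivers who begin coaching and stop for reasons other than reaching their goals. Read literally, the caregiver findings on objective 3 would come from completers only.

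Those findings may then be biased. Upward is the likelier direction, on the judgement that caregivers who found OPC unhelpful or burdensome are more likely to leave. That judgement is not a figure from the documents. The bias is nil if nobody withdraws or if leavers are as satisfied as completers. With 16 due to be treated, each caregiver not interviewed is 6.25% of the group. A qualitative account has the same selection problem as a percentage would, because themes that explain leaving would be missing. This is a cheap improvement to the plan and does not undermine the study.

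**What to change.** Reword item 11 along these lines: *Every caregiver who attended at least one coaching session will be invited to the interview, after the last session or at withdrawal.* In the report, give the number interviewed out of the number who started coaching, separately for completers and withdrawers. That requires stating what counts as completion.

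The cost is one sentence and a few extra interviews by existing staff, or none if nobody withdraws. Some withdrawers will decline, so the selection is reduced but not removed. Reporting the two counts lets a reader judge how much remains.

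### Objective 1 asks for a level of caregiver belief, but the stated analysis of its apparent measure (BIGSS) is only a correlation matrix, which at 16 to 20 caregivers is also too imprecise to define a future RCT's endpoints by itself

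*Combined protocol and SAP*

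**What the plan says.** Specific Aims, Objective 1: "To determine the degree to which caregivers of youth with SCI believe in their ability to create and achieve meaningful participation goals".

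BIGSS is neither spelled out nor mapped to an objective. Table 1 schedules it at sessions 1 and 10, alongside the COPM. Its analysis is item 2 under Secondary Exploratory in Data Handling and Analysis: "We will calculate Spearman rank correlation coefficients". The matrix relates caregivers' "confidence in achieving goals" to COPM goal attainment, parent competency, stress, anxiety, participation, the child's participation as the parent sees it, and caregiver and child characteristics.

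The item then states the use of the matrix: "We will use these associations to better define inclusion and exclusion criteria for a future RCT on OPC", and also "to define primary and secondary endpoints for a future RCT".

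Elsewhere the plan does specify other kinds of output. For the primary outcome: "We will examine changes in COPM performance and satisfaction scores using non-parametrics". Item 3 (Fidelity) lists mean, mode and range for the number of sessions, and item 4 asks for 95% confidence intervals on the intraclass correlations. No summary, change or interval is stated for BIGSS.

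On numbers, Data Collection and Study Procedures item 2 plans 16 treated caregivers, and the Sample paragraph allows up to 20.

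**The concern.** There are two linked problems.

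First, a degree of belief is a level, and a correlation matrix describes how variables move together. A sample in which everyone is confident and one in which nobody is can produce the same matrix. An analyst who follows the text would finish without a number for Objective 1, although the scores have been collected.

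Second, the same matrix is given a decision to support. A feasibility study exists to shape the next trial. If an endpoint is chosen because it showed a large correlation in 16 caregivers, the choice may rest largely on chance, and the larger trial inherits it.

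**Working it through.** **Inputs.** Planned number treated: 7 face to face + 9 phone = 16, which reproduces the stated total (Data Collection and Study Procedures, item 2). Maximum: 20 (Sample). The documents give no SD, scale, alpha or precision target for BIGSS. Two-sided 95% is assumed throughout.

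**Step 1: which instrument serves Objective 1?** The wording "confidence in achieving goals" under the BIGSS heading points to BIGSS. The rival is the PSOC, which item 10a calls the "most widely used measure of parental self-efficacy". The analysis section does not name the PSOC; it presumably enters as parent competency, which also appears only in the matrix. The COPM rates performance and satisfaction, not belief. The exit interview (Table 2) asks how successful caregivers expect to be, but gives no numeric degree. Whichever candidate is meant, no summary of level is stated.

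**Step 2: does the matrix carry a level?** Spearman's coefficient depends only on ranks. Adding a constant c to every score leaves the ranks, and so r_s, unchanged. In a simulated sample of 16, adding 3 to every score left r_s at 0.5618 before and after.

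**Step 3: precision of each correlation.** The Bonett-Wright interval is tanh( atanh(r_s) ± 1.96 × √[(1 + r_s²/2)/(n − 3)] ).

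For r_s = 0.50 and n = 16, atanh(0.50) = 0.549 and the standard error is √(1.125/13) = 0.294. The limits on the transformed scale are 0.549 ± 0.577, which back-transform to -0.03 and 0.81.

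| Observed r_s | 95% CI, n=16 | 95% CI, n=20 |
|---|---|---|
| 0 | -0.50 to 0.50 | -0.44 to 0.44 |
| 0.30 | -0.24 to 0.70 | -0.17 to 0.66 |
| 0.50 | -0.03 to 0.81 | 0.05 to 0.78 |
| 0.70 | 0.25 to 0.90 | 0.32 to 0.88 |

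**Step 4: what chance alone produces.** The number of variables is open because the characteristics are not listed, so 7 to 10 is assumed. That gives 7×6/2 = 21 to 10×9/2 = 45 pairs. In 10,000 simulated rank matrices of independent variables, the median of the largest |r_s| was 0.54 (7 variables) to 0.60 (10 variables) at n=16, and 0.48 to 0.54 at n=20. At n=16, 67% to 91% of matrices had at least one pair beyond the two-sided 5% critical value of 0.50.

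**Step 5: what a summary of level would deliver.** A distribution-free CI for the median uses binomial(n, 0.5) order statistics. At n=16 it runs from the 4th to the 13th ordered score (coverage 97.9%), and at n=20 from the 6th to the 15th (95.9%). For normally distributed scores the mean half-width, by simulation, is about 0.76 SD at n=16 and 0.59 SD at n=20. That is wide, but it addresses the question Objective 1 asks.

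**The case against.** The strongest reply is that this is a short plan for a feasibility study and the item is headed exploratory. Silence on a median does not forbid one: the scores go into the study database and anyone can summarise them. That stands in part. A reader might infer that Objective 1 cannot be answered from this study. The documents do not support that, because the data are scheduled; what is missing is a stated analysis. But the plan names descriptive output where it wants it, for sessions and for the COPM, so an implied BIGSS summary is not a safe reading.

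It is also fair that the link from BIGSS to Objective 1 is inferred, and that "confidence in achieving goals" covers achieving goals while the objective also covers creating them. Step 1 shows that the gap does not depend on the link.

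A reader might further infer that the matrix alone will fix the future endpoints. The text does not say so. Objective 5 looks at how completely and validly the instruments are filled in, Objective 6 sets further RCT parameters, and for eligibility the wording is only incremental. The remaining difficulty is that the endpoint clause has no such qualifier, and no other source is tied to that choice.

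Nor are the correlations worthless: an observed 0.70 excludes zero at both sample sizes, and 0.50 does so at n=20. Overlap between two rows of the table is not a test of their difference either, since correlations from the same caregivers are dependent.

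Finally, coaching may end early (item 4d) while Table 1 puts the closing COPM and BIGSS at session 10. One might conclude that closing scores are lost for early finishers. That is not established: for the COPM, item 9a says "Goals will be rated by the caregivers before and after coaching", and Table 1 is described as general content. It is a separate clarification and adds no weight here.

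**Conclusion.** The point holds as a gap in the stated analysis and an over-strong statement of use. Objective 1 asks for a level, and no analysis of level is stated for BIGSS or for the likely alternative. The correlations from 16 to 20 caregivers can suggest hypotheses, but they are too imprecise to define endpoints by themselves: at n=16 even an observed 0.50 is compatible with values from about zero to 0.81, and a largest coefficient of 0.54 to 0.60 is what noise typically yields.

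This rests on three assumptions: that BIGSS (or failing that the PSOC) is the Objective 1 measure, that 7 to 10 variables enter the matrix, and that those variables are independent in the noise calculation. The intervals in Step 3 need none of these; they rest on the large-sample approximation behind the formula. The primary COPM analysis is not affected. The change should be made, and confidence in the point is moderate because the instrument link is inferred.

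**What to change.** 1. State which instrument measures Objective 1. Report its median and IQR, with a 95% CI for the median, at the first and final assessments, and give the number of caregivers without a final score.
2. Report each Spearman coefficient with its 95% CI, as item 4 of the analysis section already does for the intraclass correlations.
3. Reword the sentence on use, for example: *These associations are hypothesis-generating; they will inform, but not by themselves define, eligibility criteria or endpoints for a future RCT.*
4. As a separate minor clarification, reconcile item 4d (coaching may cease before 10 sessions) with Table 1 (closing COPM and BIGSS at session 10), so that the timing of the final assessment is clear for both instruments.

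The cost is a few lines of text, with no added instrument, visit or participant. The sponsor gives up a data-driven claim about endpoints, and the reported intervals, including those for the median, will be visibly wide.
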